7.2 Serious adverse events

7.2.1 Definition of serious adverse event

An SAE is defined as any AE (appearance of [or worsening of any pre-existing] undesirable sign[s], symptom[s] or medical conditions[s]) which meets any one of the following criteria:

- is fatal or life-threatening
- results in persistent or significant disability/incapacity
- constitutes a congenital anomaly/birth defect
- requires inpatient hospitalization or prolongation of existing hospitalization, unless hospitalization is for:
 - routine treatment or monitoring of the studied indication, not associated with any deterioration in condition
 - elective or pre-planned treatment for a pre-existing condition that is unrelated to the indication under study and has not worsened since signing the informed consent
 - treatment on an emergency outpatient basis for an event not fulfilling any of the definitions of a SAE given above and not resulting in hospital admission
 - social reasons and respite care in the absence of any deterioration in the patient's general condition
- is medically significant, e.g., defined as an event that jeopardizes the patient or may require medical or surgical intervention. All malignant neoplasms will be assessed as serious under "medically significant" if other seriousness criteria are not met.

Life-threatening in the context of a SAE refers to a reaction in which the patient was at risk of death at the time of the reaction; it does not refer to a reaction that hypothetically might have caused death if it were more severe (see ICH-E2D Guideline).

Medical and scientific judgment should be exercised in deciding whether other situations should be considered serious reactions, such as important medical events that might not be immediately life threatening or result in death or hospitalization but might jeopardize the patient or might require intervention to prevent one of the other outcomes listed above. Examples of such events are intensive treatment in an emergency room or at home for allergic bronchospasm, blood dyscrasias or convulsions that do not result in hospitalization or development of dependency or abuse (see ICH-E2D Guideline).

Any suspected transmission via a medicinal product of an infectious agent is also considered a serious adverse reaction.

7.2.2 Serious adverse event reporting

To ensure patient safety, every SAE, regardless of causality, occurring after the patient has provided informed consent and until 12 weeks following the last administration of study treatment must be reported to Novartis within 24 hours of learning of its occurrence. Any SAEs experienced after the 12-week period following the last administration of study treatment should only be reported to Novartis if the investigator suspects a causal relationship to study treatment.

All follow-up information for the SAE including information on complications, progression of the initial SAE and recurrent episodes must be reported as follow-up to the original episode within 24 hours of the investigator receiving the follow-up information. An SAE occurring at a different time interval or otherwise considered completely unrelated to a previously reported one must be reported separately as a new event.

Information about all SAEs is collected and recorded on the Serious Adverse Event Report Form; all applicable sections of the form must be completed in order to provide a clinically thorough report. The investigator must assess the relationship of each SAE to each specific component of the study treatment (if the study treatment consists of several components) complete the SAE Report Form in English, and submit the completed form within 24 hours to Novartis. Detailed instructions regarding the submission process and requirements for signature are to be found in the investigator folder provided to each site.

Follow-up information is submitted as instructed in the investigator folder. Each re-occurrence, complication, or progression of the original event must be reported as a follow up to that event regardless of when it occurs. The follow-up information should describe whether the event has resolved or continues, if and how it was treated, and whether the patient continued or withdrew from study participation.

If the SAE is not previously documented in the Investigator Brochure or Package Insert (new occurrence) and is thought to be related to the study treatment a Drug Safety and Epidemiology Department associate may urgently require further information from the investigator for health authority reporting. Novartis may need to issue an Investigator Notification to inform all investigators involved in any study with the same study treatment that this SAE has been reported. Suspected Unexpected Serious Adverse Reactions will be collected and reported to the competent authorities and relevant ethics committees in accordance with EU Guidance 2011/C 172/01 or as per national regulatory requirements in participating countries.

7.3 Liver safety monitoring

Not applicable.

7.4 Renal safety monitoring

Not applicable.

7.5 Reporting of study treatment errors including misuse/abuse

A medication error is an unintended failure in the drug treatment process that leads to, or has the potential to lead to, harm to the patient (EMA/762563/2014).

Misuse refers to situations where the medicinal product is intentionally and inappropriately used not in accordance with the protocol.

Abuse corresponds to the persistent or sporadic, intentional excessive use of a medicinal product, which is accompanied by harmful physical or psychological effects.

Study treatment errors and uses outside of what is foreseen in the protocol will be collected in the dose administration record eCRF irrespective of whether or not associated with an AE/SAE and reported to Safety only if associated with an SAE. Misuse or abuse will be collected and reported in the safety database irrespective of it being associated with an AE/SAE.

Treatment error type	Document in DAR eCRF (Yes/No)	Document in AE eCRF	Complete SAE form
Unintentional study treatment error	Yes	Only if associated with an AE	Only if associated with an SAE
Misuse/abuse	Yes	Yes	Yes, even if not associated with a SAE

DAR = dose administration record

7.6 Pregnancy reporting

To ensure patient safety, each pregnancy occurring after signing the informed consent must be reported to Novartis within 24 hours of learning of its occurrence. The pregnancy should be followed up to determine outcome, including spontaneous or voluntary termination, details of the birth, and the presence or absence of any birth defects, congenital abnormalities, or maternal and/or newborn complications.

Pregnancy must be recorded on the Pharmacovigilance Pregnancy Form and reported by the investigator to the local Novartis Drug Safety and Epidemiology Department. Pregnancy follow up should be recorded on the same form and should include an assessment of the possible relationship to the study treatment.

Any SAE experienced during the pregnancy and unrelated to the pregnancy must be reported on a SAE Report Form.

Pregnancy outcomes should be collected for the female partner of any male who take study treatment in this study. Consent to report information regarding these pregnancy outcomes should be obtained from the female partner.

7.7 Prospective suicidality assessment

Not applicable.

8 Data review and database management

8.1 Site monitoring

Before study initiation, at a site initiation visit or at an investigator's meeting, a Novartis representative will review the protocol and eCRF with the investigators and their staff. During the study, the field monitor will visit the site regularly to check the completeness of patient records, the accuracy of entries on the eCRF, the adherence to the protocol and to Good Clinical Practice (GCP) and the progress of enrollment. Key study personnel must be available to assist the field monitors during these visits.

The investigator must maintain source documents for each patient in the study, consisting of case and visit notes (hospital or clinic medical records) containing demographic and medical information, laboratory data, ECGs, and the results of any other tests or assessments. All information on eCRFs must be traceable to these source documents in the patient's file. The investigator must also keep the original informed consent form signed by the patient (a signed copy is given to the patient).

The investigator must give the monitor access to all relevant source documents to confirm their consistency with the eCRF entries. Novartis monitoring standards require full verification for the presence of informed consent, adherence to the inclusion/exclusion criteria, documentation of SAEs, and of data that will be used for all primary variables. Additional checks of the consistency of the source data with the eCRF are performed according to the study-specific monitoring plan. No information in source documents about the identity of the study patients will be disclosed.

8.2 Data collection

Designated investigator staff will enter the data required by the protocol into the OC/RDC system. Designated investigator site staff will not be given access to the system until they have been trained.

Automatic validation procedures within the system check for data discrepancies during and after data entry and, by generating appropriate error messages, allow the data to be confirmed or corrected online by the designated investigator site staff. The investigator must certify that the data entered into the eCRFs are complete and accurate. After database lock, the investigator will receive copies of the patient data for archiving at the investigational site.

8.3 Database management and quality control

Novartis staff (or designated Contract Research Organization [CRO] staff) review the data entered into the eCRFs by investigator/qualified site staff for completeness and accuracy and instruct the investigator/qualified site staff to make any required corrections or additions. Queries are sent to the investigational site using an electronic data query. Investigator/qualified site staff is required to respond to the query and confirm or correct the data. If the electronic query system is not used, a paper Data Query Form will be faxed to the site. Investigator/qualified site staff will complete and sign the faxed copy and fax it back to Novartis staff that will make the correction to the database. The signed copy of the Data Query Form is kept at the investigator/qualified site staff site.

Concomitant medications entered into the database will be coded using the World Health Organization (WHO) Drug Reference List, which employs the Anatomical Therapeutic Chemical classification system. Concomitant procedures, non-drug therapies and AEs will be coded using the Medical dictionary for regulatory activities (MedDRA) terminology.

Laboratory samples will be processed centrally and the results will be sent electronically to Novartis (or a designated CRO).

Patient-reported outcomes data will be collected from all patients. These data will be processed centrally and the results will be sent electronically to Novartis (or a designated CRO) or transferred by investigator/qualified site staff into the eCRF, respectively.

Randomization codes, data about study treatments dispensed to the patient, all IRT recorded dosage changes, and some efficacy data will be tracked using IRT. The system will be supplied by a vendor that will also manage the database. The database will be sent electronically to Novartis (or a designated CRO).

Each occurrence of a code break via IRT will be reported to the clinical team and monitor. The code break functionality will remain available until study shut down or upon request of Novartis.

8.4 Data Monitoring Committee

The implementation of a Data Monitoring Committee to review the safety data of this study is not planned. However, a Scientific Steering Committee is formed. The task of the Committee is to safeguard proper execution of the study and monitor the progress.

8.5 Adjudication Committee

Not required.

9 Data analysis

9.1 Analysis sets

The following analysis sets will be used:

- **Full analysis set:** The FAS will be comprised of all patients who were randomized to the study. Following the intent-to-treat principle, patients will be analyzed according to the treatment assigned at baseline
- **Safety set (SAF):** The safety set includes all patients who took at least one dose of study treatment during the Treatment Epoch, whether or not they were randomized. Patients will be analyzed according to the treatment received

The treatment arms (see [Section 5.2](#)) for the analyses of data will include:

Main Study

- Sixty-eight patients from Arm A1a and 12 from Arm A1b
- Sixty-eight patients from Arm B1a and 12 from Arm B1b

Mechanistic Sub-study

- Twelve patients from Arm A1b
- Twelve patients from Arm A2
- Twelve patients from Arm B1b
- Twelve patients from Arm C1
- Twelve patients from Arm C2

9.2 Patient demographics and other baseline characteristics

Demographics and baseline characteristics

Summary statistics will be presented for continuous demographic and baseline characteristic variables for each treatment arm and for all patients in the FAS. The number and percentage of patients in each category will be presented for categorical variables for each treatment arm and for all patients.

Medical history

Any condition entered as medical history or current medical conditions at baseline will be coded using the MedDRA dictionary. Medical history will be summarized for all patients in the FAS by system organ class and preferred term in the MedDRA dictionary. Summaries for psoriasis-specific medical history will be provided.

Cardiovascular medical history assessed prior to randomization will also be summarized.

9.3 Treatments

The analysis of study treatment data will be based on the SAF. The duration of exposure to study treatment will also be summarized by treatment arm.

Prior and concomitant treatments

Prior and concomitant treatments will be summarized by treatment arm in separate tables for the SAF and for the treatment epochs separately.

Prior treatments are defined as treatments taken and stopped prior to the first dose of study treatment. Any treatment given at least once between the day of first dose of randomized study treatment (baseline) and the last study visit will be a concomitant treatment, including those which were started pre-baseline and continued into the Treatment Epoch.

Treatments will be presented in alphabetical order, by ATC codes and main groups. Tables will also show the overall number and percentage of patients receiving at least one treatment of a particular ATC code and at least one treatment in a particular anatomical main group.

In addition, medical procedures and significant non-drug therapies as coded in MedDRA will be summarized.

9.4 Analysis of the primary variable

The primary objective of this study is to demonstrate the superior efficacy of secukinumab 300 mg s.c. compared to nb-UVB in patients with new-onset moderate to severe plaque psoriasis with respect to patients achieving PASI 90 response at Week 52.

9.4.1 Primary variable

The primary efficacy variable is the proportion of patients who achieve PASI 90 at Week 52. The analysis for the primary objective will be based on the FAS.

9.4.2 Statistical model, hypothesis, and method of analysis

For the primary analysis, the following hypothesis testing will be performed:

$$H_{01}: p_{sec} = p_{nbUVB} \text{ versus } H_{A1}: p_{sec} > p_{nbUVB}$$

where p_{sec} and p_{nbUVB} are the proportion of PASI 90 responders in the secukinumab 300 mg s.c. (Arm A1) and nb-UVB (Arm B1) groups, respectively.

The primary analysis method for PASI 90 response at Week 52 will use a logistic regression model with treatment as an explanatory variable and significant covariates among baseline PASI score, age, and body mass index. The best subset of the significant covariates will be selected using a forward selection method based on the likelihood ratio test. Interaction terms will also be considered, if significant, among the best subset of selected covariates and the treatment term.

Statistical significance will be evaluated at a 1-sided alpha level of 0.025. The estimated adjusted odds ratio for Arm A1 versus Arm B1 will be displayed along with the associated 2-sided 95% confidence interval (equivalent to the 1-sided 97.5% confidence interval) and p-value.

If there are issues related to the convergence of the logistic regression model, the above hypothesis will be tested using a Wald test.

The primary analysis is not expected to be influenced by the use of topical treatment within the first 4 weeks since, any effect will be worn off by Week 52.

9.4.3 Handling of missing values/censoring/discontinuations

Missing data will be handled with a modified multiple imputation method. Patients who discontinued the study before Week 52 because of lack of efficacy or AEs will be considered non-responders. Missing values for other reasons will be inserted by means of the multiple imputation method.

The multiple imputation method is a simulation-based approach where missing values are replaced by multiple Bayesian draws from the conditional distribution of missing data given the observed data and covariates, creating multiple completed data sets, which can then be analyzed using standard methods. Rubin (1987) presented rules how to combine the multiple sets of estimates to produce overall estimates and confidence intervals that adequately incorporate missing data uncertainty.

Missing values for the “change from baseline PASI score” will be imputed simultaneously based on an underlying normal distribution and using the data augmentation procedure of Markov Chain Monte Carlo (MCMC) method. The change from baseline in PASI score appears to follow closer to a normal distribution than the actual PASI score. The imputations will be done separately for each treatment group. Further details will be provided in the statistical analysis plan.

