5.5.1 Patient numbering

Each patient is uniquely identified by a Patient Number which is composed by the 4-digit site number assigned by Novartis and a 3-digit sequential number assigned by the investigator (e.g., Patient █ at Site █ will be assigned Patient Number █). Once assigned to a patient, the Patient Number will not be reused.

Upon signing the informed consent form, the investigator will assign the patient the next sequential number. The investigator or his/her staff will contact the IRT and provide the requested identifying information to register the patient into the IRT. The site must select the electronic Case Report Form (eCRF) book with a matching Patient Number from the Electronic Data Capture system to enter data.

If the patient fails to be treated for any reason, the IRT must be notified within 2 days that the patient was not treated. The reason for not being treated will be entered on the Screening Epoch Disposition eCRF page.

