9.5.2 Investigator's global assessment mod 2011

The secondary efficacy variable is the proportion of all randomized patients who achieve at least IGA 0/1 response at Week 52. Patients will be considered responders if they achieve a score of 0/1 and improve by at least 2 points compared with baseline.

This analysis will be based on the FAS.

The method for IGA 0/1 response at Week 52 will use a logistic regression model similar to the primary analysis, with treatment as an explanatory variable and the significant variables among baseline IGA score, age, and body mass index, and their interactions with treatment. Forward selection procedure based on the likelihood ratio test would be used to select the best subset of covariates. The estimated adjusted odds ratio for Arm A1 versus Arm B1 will be displayed along with the associated 95% confidence interval.

If there were issues related to the convergence of the logistic regression model, the above hypothesis will be tested using a 1-sided Wald test.

Missing IGA 0/1 response values will be imputed with non-response regardless of the reason for the missing data (e.g., premature study discontinuation, missed visit, or administrative issue).

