2.2 Analysis sets

The following analysis sets will be used:

Randomized set: The randomized set will be defined as all subjects who were randomized at Baseline Visit. Unless otherwise specified, misrandomized subjects will be excluded from the randomized set.

Misrandomized subjects are subjects who are screen failures, but have been randomized by the investigator before eligibility was finally assessed, however have not been treated. If subjects were re-screened and successfully randomized, they will be included in the randomized set according to the treatment assigned in the last randomization.

Full analysis set (FAS): The FAS will be comprised of all subjects who were randomized to the study. Following the intent-to-treat principle, subjects will be analyzed according to the treatment assigned at Baseline.

Modified full analysis set (mFAS): The mFAS includes all subjects who are randomized and took at least one dose of study treatment during the Treatment Phase, subjects will be analyzed according to the treatment assigned at Baseline.

Safety set (SAF): The safety set includes all subjects who took at least one dose of study treatment during the Treatment Phase, whether or not they were randomized. Subjects will be analyzed according to the treatment received.

[Section 2.15.2](#) define the analysis set used for additional analysis.

Protocol deviations leading to exclusion from analysis sets are defined in Section 5.7.

The treatment arms for the analyses of data will have the following distribution of subjects:

Main Study (Planned number)

- Eighty subjects from Arm A1 (i.e., A1a(68)+A1b(12))
- Eighty subjects from Arm B1 (i.e., B1a(68)+B1b(12))

Mechanistic Sub-study (Planned number)

- Twelve subjects from ArmA1b
- Twelve subjects from Arm A2
- Twelve subjects from Arm B1b
- Twelve subjects from Arm C1
- Twelve subjects from Arm C2

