For the Mechanistic Sub-study, additional 12 randomized subjects will be treated for 104 weeks with secukinumab 300 mg s.c. (Arm A2), along with 12 subjects each from Arm A1b and Arm B1b, and will serve as active groups. Further, 12 subjects identified with chronic plaque psoriasis will be allocated to secukinumab 300 mg s.c. for 52 weeks (Arm C1) and another 12 subjects with chronic plaque psoriasis will be treated during 104 weeks with secukinumab 300 mg s.c. (Arm C2), both serving as control groups for the Mechanistic Sub-study. As the Mechanistic Sub-study will not involve any formal testing of hypothesis, the sample size for it is obtained in an illustrative manner.

4 Change to protocol specified analyses

In Study design section , under follow up subsection “PASI90 score” is mentioned in the protocol however it is updated as “PASI90 response”.

Randomized set is added.

[REDACTED]

PASI 75 is added in the section [2.13.2.1](#) and [2.14](#).

[REDACTED]

A new population called Modified full analysis set (mFAS) is introduced. Randomized subjects who received treatment are considered in this population. Primary, key secondary and additional secondary endpoints will be analysed using mFAS along with FAS. [REDACTED]

[REDACTED]

Statistical analysis for Week 156 will be performed at the actual scheduled visit Week 152.

5 Appendix

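### Eligible patients who are randomized but never treated stay in the FAS, and their missing Week 52 PASI is imputed from a by-arm model fitted essentially to treated patients

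*Protocol*

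**What the plan says.** **Who is in the FAS.** Protocol 9.1: "The FAS will be comprised of all patients who were randomized to the study", analysed as assigned. SAP 2.2 repeats this, and Table 5-2 in SAP 5.7 removes only misrandomized subjects. SAP 2.2 describes these as screen failures who "have been randomized by the investigator before eligibility was finally assessed, however have not been treated". Having taken no study treatment is a ground for exclusion only from the safety set and the mFAS.

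**The treated-only set.** SAP 2.2: "The mFAS includes all subjects who are randomized and took at least one dose of study treatment during the Treatment Phase". SAP section 4 introduces it as a change from the protocol: "Randomized subjects who received treatment are considered in this population". SAP 2.3.2.2 falls back on the randomization date when there is no treatment start date.

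**Missing PASI at Week 52.** Under Protocol 9.4.3 and SAP 2.5.3, only patients who left the study for lack of efficacy or adverse events are set to non-response. For the rest, "Missing values for other reasons will be inserted by means of the multiple imputation method". "The imputations will be done separately for each treatment group", and the SAP adds baseline PASI, age and BMI to the model and names the MAR assumption.

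**Missing PASI at Week 104.** Protocol 9.5.1 uses the same method and adds relapse as non-response. SAP 2.6.3 further adds patients who did not reach PASI 50 at Week 52.

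**IGA 0/1.** Protocol 9.5.2 (likewise SAP 2.7.1): "Missing IGA 0/1 response values will be imputed with non-response regardless of the reason for the missing data".

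**Untreated patients in the conduct sections.** Protocol 5.5.1: "If the patient fails to be treated for any reason, the IRT must be notified within 2 days that the patient was not treated". Sites record why on the Screening Epoch Disposition page. Protocol 6.1 classes anyone who consents but stops before the first administration as a screening failure.

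**The concern.** An eligible patient who is randomized and then never receives a dose or an nb-UVB session has not left for lack of efficacy or an adverse event. No rule names this patient, so a missing Week 52 PASI falls into the residual category and is multiply imputed. The patient contributes only baseline PASI, age and BMI. The PASI changes that inform the draws come essentially from treated patients of the assigned arm.

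MAR is hard to defend here. The reason for the missing value, no treatment, bears directly on the outcome and is not in the imputation model. The FAS estimate then credits PASI 90 responses to people who never started the therapy, and it is pulled towards the mFAS estimate that it should serve to check. The IGA analysis treats the same patient in the opposite way, and neither document explains the difference. Allocation is open-label, so non-starts may differ between arms.

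**Working it through.** **1. The plan's own figures.** Inputs from Protocol 9.8 and 9.9: 80 per arm, 1-sided alpha 0.025, PASI 90 of 70% v 28% at Week 52 (28% = 35% x 0.8) and 21% v 4% at Week 104 (23% x 0.93 = 21.4%; 5% x 0.84 = 4.2%).
- Week 52: power is 99.99% (pooled test) or 99.995% (unpooled Wald), against the stated 99.9%.
- Week 104: exact 1-sided Fisher power is 90.0%, against the stated figure of around 89%.

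Both reproduce. Neither calculation allows for never-treated patients.

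**2. Shift in the Week 52 difference.** Let u be the number never treated with no Week 52 PASI, and p the probability that imputation makes such a patient a responder. Compared with non-response:

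shift = (u_A1 x p_A1 - u_B1 x p_B1) / 80

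The documents give no u; four is an assumption, so each arm moves by 4/80 = 5% of its p. They give no p either. Four sets of rates were tried:
- An illustrative normal-model imputation by arm, for patients with baseline data only, with true response of 70% and 28% and assumed PASI distributions: 42% in A1, 18% in B1.
- A second simulation with BMI, age, baseline PASI and the changes at Weeks 16 to 52, true response of 70% and 34-36%, and three assumed spreads: 48-56% and 30-32%.
- The planning rates before dropout: 70% and 35%.
- The planning rates after dropout: 70% and 28%.

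| p in A1 / B1 | 4 in A1 only | 4 in B1 only | 4 in each arm |
|---|---|---|---|
| 42% / 18% | +2.1 | -0.9 | +1.2 |
| 48-56% / 30-32% | +2.4 to +2.8 | -1.5 to -1.6 | +0.8 to +1.3 |
| 70% / 35% | +3.5 | -1.75 | +1.75 |
| 70% / 28% | +3.5 | -1.4 | +2.1 |

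Values are percentage points. Example: 4 x 0.42/80 = 2.1 and 4 x 0.18/80 = 0.9, net 1.2. The first and third rows give the quoted range of about 1.2 to 1.8; all pairings together give 0.8 to 2.1. In both simulations the normal model brings p below the true response rate, but a clear arm difference remains.

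**3. Effect of counting them as non-responders, from 70% v 28%.** Each rate becomes p x (1 - u/80).

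| Never treated | Week 52 rates | Difference | Odds ratio | Wald power |
|---|---|---|---|---|
| none | 70.0% v 28.0% | 42.0 | 6.00 | 99.995% |
| 4 in each arm | 66.5% v 26.6% | 39.9 | 5.48 | 99.98% |
| 8 in each arm | 63.0% v 25.2% | 37.8 | 5.05 | 99.94% |
| 8 in A1 only | 63.0% v 28.0% | 35.0 | 4.38 | 99.7% |
| 8 in B1 only | 70.0% v 25.2% | 44.8 | 6.93 | above 99.9% |

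**4. Week 104.** Under Protocol 9.5.1 the same gap exists. At the plan's 21% and 4%, four per arm would add 4 x 0.21/80 = 1.05 points in A1 and 4 x 0.04/80 = 0.2 in B1, net 0.85. Under SAP 2.6.3 there are two readings. If a missing Week 52 PASI means that PASI 50 was not achieved, the patient is already a non-responder. If the rule is applied to imputed Week 52 values, the patient is a non-responder only in the completed data sets where the draw falls below PASI 50. The SAP does not say which.

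Counting never-treated patients as non-responders changes Fisher power from 90.0% to 88.0% (four per arm), 85.6% (eight per arm), 82.5% (eight in A1 only) or 92.1% (eight in B1 only).

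**The case against.** **Such patients may not be in the FAS at all.** Protocol 6.1 calls them screening failures, Protocol 5.5.1 records them on a screening page, and the SAP drops randomized but untreated screen failures from the FAS. This has force, but the SAP exclusion is limited to patients randomized before eligibility was settled. It does not cover an eligible patient who declines after learning the allocation, and an mFAS alongside the FAS suggests that some untreated patients are expected to remain. What stands is an ambiguity that the plan should resolve.

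**The plan already has safeguards.** Protocol 9.4.4 and SAP 2.5.4 plan non-responder imputation at Week 52 whatever the reason, and SAP 2.5.4 and 5.6.1.2 add a tipping-point analysis that varies the missing responses by arm. These show the effect at Week 52. They are supportive and leave the main FAS analysis unchanged. Non-responder imputation is not named for the H02 test in SAP 2.6, and the repeats up to Week 104 in SAP 2.5.4 use the mFAS, which omits these patients. The mFAS is itself a post-randomization exclusion in an open-label trial, and SAP 2.5.1 does not say whether FAS or mFAS decides.

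**MAR imputation is a legitimate choice.** A reader might infer that the FAS analysis is no longer intention-to-treat. That goes too far: everyone randomized is kept and analysed as assigned. The dispute is over the value given to one kind of missing outcome.

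**Few non-starts are likely in A1.** Protocol 5.3 and 5.5.4 place randomization and first administration at the same baseline visit, with the first secukinumab dose given on site. This supports a small number in A1 and is one reason not to assume a direction.

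**Conclusion.** The gap is real and small. A never-treated FAS patient with no Week 52 PASI is credited with response at, or somewhat below, the treated rate of the assigned arm. If four per arm are assumed, the Week 52 difference rises by about 1.2 to 1.8 points (0.8 to 2.1 over all rates tried). Four in A1 only raise it by about 2.1 to 3.5, and four in B1 only lower it by about 0.9 to 1.8. The counts are assumptions, and the simulated rates rest on assumed PASI distributions.

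Three stronger readings are not supported:
- *That the rule favours secukinumab.* This holds for equal numbers in the two arms or for non-starts in A1. Non-starts mainly in B1 would favour nb-UVB, and the documents do not say where they fall.
- *That the primary conclusion is at risk.* Planning power for H01 stays above 99% in every scenario computed.
- *That H02 necessarily has the same problem.* It does under Protocol 9.5.1; under SAP 2.6.3 the PASI 50 rule may already settle it.

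**What to change.** Add to Protocol 9.4.3 and 9.5.1 and to SAP 2.5.3 and 2.6.3: *FAS patients who received no study treatment and whose PASI is missing at Week 52 (or Week 104) are non-responders at that visit; multiple imputation is used only for patients who started study treatment; observed values are kept.* Apply it in each completed data set before the logistic model. The restriction to missing PASI matters, because a rule for all untreated patients would override real observations.

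Two clarifications belong with it:
- Reconcile the screening-failure wording in Protocol 6.1 with the FAS in Protocol 9.1 and the misrandomized and FAS definitions in SAP 2.2 and Table 5-2.
- State in SAP 2.6.3 that a never-treated patient with no Week 52 PASI is a Week 104 non-responder unless a Week 104 PASI is observed.

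The cost is one sentence and one programming line, with slightly lower response rates in any arm that has such patients. SAP 2.14.1 says that the Week 52 report has been prepared, and SAP 2.15 that Week 104 results have been seen. A change made now should therefore be reported as a post hoc FAS analysis beside the planned one, with the number never treated shown by arm.
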